Adverse Event Form (SAFTEE): In order to monitor adverse events from the study interventions, the SAFTEE will be administered before and after each session. This is a locally developed symptom checklist that includes possible side effects of study medications and/or procedures and has been used in our previous studies

Visual Analog Scale - Anxiety (VASA). Anxiety levels will be measured using a self-report VASA. Participants will be asked to rate their level of anxiety, how "anxious, tense and/or jittery" they feel at that particular moment. Their responses can range from 1="not at all" to 10="extremely high".

Visual Analog Scale - Craving (VASC). Current craving for alcohol will be measured using a self-report VASA. Participants will be asked to rate their level of craving, "desire for a drink" they feel at that particular moment. Their responses can range from 0="not at all" to 10="extremely high".

The Differential Emotions Scale-Revised short form (DES-R)[94] will be used as a measure of subjective emotional experience. The measure consists of a number of subscale and for the present study we will use five subscales: sadness, anger, joy, fear, and anxiety. Each subscale is made up of 5 adjectives describing the particular emotion state. Participants rate on a 5-point scale the extent to which each word describes how they feel at the present moment. The DES shows good psychometric properties.[94] The DES has been used to examine subjective emotion following laboratory mood inductions.[88]

Impulsivity will be assessed through the Balloon Analogue Risk Task (BART) [50]and Barrett Impulsivity Scale (BIS) [51]. The Go/No-Go Task will assess the ability to withhold responses to an infrequently occurring target (No-Go trials). A series of blue and green rectangular shapes are presented every 1150 ms and participants are instructed to press a spacebar every time the green rectangular shape appeared, and to give equal importance to speed and accuracy. The primary outcome is the number of errors on the No-Go trials[95, 96].

State-Trait Anxiety Inventory (STAI) will be used to assess anxiety symptoms; the full version will be used at the start of the lab session and the shorter version (STAI-6) will be used for all other indicated timepoints [97].

V.6 05Jun2020 18

6.J.6. Physiological Measures: BP and HR will be assessed using an automatic blood pressure cuff.

6.K. Statistical Plan and Power Analysis:

- **6.K.1. Procedures:** Procedures for the monitoring and analysis of data were developed during previous clinical trials conducted at Yale and will be overseen by Drs. [name] and [name].
- 6.K.1.a. To Examine the Efficacy of ZNS (Specific Aim 1), Primary Outcome: We will use *drinks per week* as the primary outcome variable. This is also the primary outcome we are using for veteran ZNS study, and is one that can be readily applied when combining the samples. Recently the NIAAA and FDA Alcohol Clinical Trials Initiative (ACTIVE: a workgroup of experts in the field tasked with optimizing alcoholism clinical trials outcomes and methods) has suggested that for medication development trials and small to medium size trials, continuous outcome variables such as drinks/week or heavy drinking days per week are optimal as opposed to categorical outcomes. We will use a mixed models approach to examine for a statistically significant difference in drinks per week and on continuous secondary outcome variables. The model will include fixed effects for medication group, week, and the interaction between medication and week. We will include pre-treatment drinking behavior (past month HDD) as a covariate and will select the best-fitting variance-covariance structure based on Schwartz-Bayesian Information criterion (BIC). We will incorporate a grace period corresponding to the time it takes to titrate the medication to target dose into the models, and we will focus the primary analysis on the last 8 weeks of treatment at the target dose. All of these outcomes can be obtained from the TLFB data, and from the daily drinking data obtained from the IVR.

An important initial consideration in considering efficacy will be to identify baseline differences between groups that may have occurred despite randomization. A successful outcome during the treatment trial will be defined in terms of a statistically significant difference on the primary outcome measure: drinks per week, compared during the 8 weeks of active treatment at the target dose, allowing for an 8 week grace period for the medication titration. For all analyses, heavy drinking days will be defined as follows; for men > 4 drinks in a day and for women > 3 drinks in a day. Patients will be followed irrespective of whether they continue to receive medication treatment, so that analysis will include all data available for the 8-week treatment period. All analyses will be **intent-to-treat**. The α will be set at .05 for the primary outcome variable. Between site differences will be explored. We will test interaction effects of GRPS in the regression models for the primary/secondary outcomes (**Exploratory Aim 1**), testing the hypothesis that ZNS's effect on drinking is greater in those with higher GRPS.

6.K.2 Secondary outcome measures: We will use a mixed models approach to examine for a statistically significant difference on heavy drinking days (HDD) per week, changes in GGTP level, measures of alcohol urge/craving (AUQ), and alcohol-related problems (as measured on the SIP). For each of these outcome measures, the model will include fixed effects for medication group, week, and the interaction between medication and week. We will include pre-treatment drinking behavior (past month HDD) as a covariate and will select the best-fitting variance-covariance structure based on Schwartz-Bayesian Information criterion (BIC). We will incorporate a grace period corresponding to the time it takes to titrate the medication to target dose into the models, and we will focus the primary analysis on the 8 weeks of treatment at the target dose. We will use the Hommel's correction for multiple comparisons on the secondary outcomes to guard against chance findings. With last secondary outcome measure percentage of subjects with no heavy drinking days (PSNHDD), we will use a logistic regression analysis with PSNHDD as a categorical dependent variable. Medication condition (PLC or ZNS) will be the main independent variable, and we will include the variables of civilian or veteran status. and sex as covariates. We will also examine the use of biomarkers (GGT, PEth) to verify and adjust subjective drinking data as these biomarkers can detect occult harmful drinking when a subject is not forthcoming.

6. K. 3. Dropouts and missing data: For the analysis of PSNHDD using logistic regression, all dropouts will be counted as relapsed. For all repeated measures analysis, we will use all V.6 05Jun2020

available data on individuals and thus dropouts provide data until the point of dropout. We will compare dropout patterns between groups and if there are concerns of informative dropout and/or informative intermittent missing data, we will use pattern mixture models [98] to perform sensitivity analyses to our main analyses. Adherence to the medication will be evaluated and controlled for in secondary analyses. We will evaluate and compare both medication conditions (PLC, ZNS) for percentage of prescribed pills taken.

- 6. K. 4. To use telephone-based daily process data collection to elucidate the mechanism of action of ZNS as it relates to changes in craving, anxiety, self-efficacy, and genetic variation (Specific Aim 2, Exploratory Aim 1): Multilevel models will be used to evaluate the associations between craving, self-efficacy, anxiety, and daily drinking and how these associations vary as a function of medication group and GRPS. Similar to [name] et al. [79], we will focus on predicting nighttime drinking (i.e., drinks consumed after the early evening report), but here we will use psychological measures reported during the early evening in the daily survey. Nighttime drinking levels will be determined by subtracting the number of drinks consumed during the current day from the total number of drinks consumed for that day (reported the following day). We will follow the general analysis scheme used by [name] et al. [79], but will use mixed effects/multilevel models, rather than generalized estimating equations (GEE) models [99] because mixed models give unbiased estimates under less restrictive assumptions about missing data. We will examine the number of drinks consumed (using a Poisson model or negative binomial model if there is overdispersion). We will use the HGLM module of the HLM7 program, as it is more flexible for some of our models than PROC GLIMMIX in SAS. Analysis will focus on the last eight weeks of treatment, consistent with the analyses of outcomes in Aim 1. We will test the hypothesis that ZNS reduces nighttime drinking and that craving, anxiety, and GRPS act as moderators of this effect. We anticipate greater ZNS effect in subjects with greater anxiety, craving and genetic loading (greater GPRS). We will examine whether ZNS's effect on drinking is mediated by self-efficacy using the approach of Kraemer et al. [100, 101], such that self-efficacy is significantly affected by ZNS treatment, and has a main or interaction effect on nighttime drinking in the model containing both treatment and the potential mediator as predictors.
- 6. K. 5. Stress Reactivity Lab (Exploratory Aim 2): We will compare pre- and post-treatment changes in levels of anxiety, craving, and impulsivity measures induced by stressful and alcohol-cue imagery in the lab. We will test if the mean induced changes are attenuated by ZNS more than placebo using ANCOVA. The amount of reactivity pre-treatment will be explored as a covariate in secondary outcome models.
- **6.K. 6. Safety:** Safety will be analyzed using categorical outcomes, defined by the type and severity of adverse effects. Summary measures of adverse events will be developed by organ system from the SAFTEE [77, 78] and will be compared for patients receiving ZNS or PLC using \Box^2 analysis or Fisher's exact tests, with an emphasis on moderate-to-severe adverse events.
- 6. K. 7. Sample Size And Power Estimate (Specific Aim 1): For continuous outcomes, based on the effect sizes from our pilot study of ZNS (showing a moderate effect size on drinks/week d=0.5, and .27 HDD/week), we estimated that a study with N=128 subjects (a 20% drop out rate) would be well powered (>.80) to detect a medium effect size difference on the secondary outcomes HDD per week and total drinks per week for the main effect of group assuming alpha level of 0.05. Based on past trials we are expecting a dropout rate < 30%. We will quantitatively examine the veteran and civilian populations for differences in variance and treatment response, and combine them (if valid) in a patient-level pooled analysis, further increasing power on all outcomes. If substantial differences are observed between the veteran and civilian samples, we will meta-analyze them. For PSNHDD, from the pilot study, in the ZNS group, 12 of 20 subjects did not relapse in the 28 days of the study, compared to 7 of 20 PLC subjects. Using this effect size, the proposed sample size of 80 subjects per group has >89% power to detect such a difference in the rates of no heavy drinking (i.e. 60% vs. 35%), assuming a two-sided alpha level of 0.05. We can also detect slightly smaller differences (60% vs. 38%, 35% vs. 57%) with 80% power under the same assumptions. Both in the estimation of effect

size from the pilot data and in the sample size analysis, dropouts are counted as relapsed to heavy drinking.

6 K. 8. Pharmacogenomic and Micro-longitudinal analyses power estimate (Aim 2, exploratory aims): There is little ZNS-specific data by which we could reasonably estimate effect sizes for these analyses. Three recent treatment studies by our group showed significant pharmacogenetic effects with samples of about 110-150 in each [15, 85, 102]. By using a mixed models approach on drinking variables, and HLM for the micro-longitudinal analyses, we will be adequately powered to detect medium-to-large effects in these analyses.

6.L. Economic Considerations: Participants will be paid a nominal but fair amount of money for their time and participation, up to \$1110 (i.e., enough money to fairly compensate and encourage follow-up without being coercive or encouraging risk taking). The payment schedule is outlined in detail below (SEE TABLE 4).

Additionally, participants can earn up to \$320 for completing the IVR phone calls (\$2 per completed phone call plus \$6 for each week where 6 or more calls are completed (up to \$20/week for 16 weeks)). If they do not have a cell phone to complete the calls we will give them one to borrow during the study which must be returned when they complete the study.

By participating in the stress labs, subjects can also earn \$40 for the script development, \$100 for each of the two stress labs (\$200 total), and up to \$40 for the computer tasks during the stress labs (up to \$20 per lab session).

If all parts of this study are completed, participants have the potential to earn up to \$1110 (this does not include the additional travel compensation mentioned earlier). This payment is for the time and effort associated with study assessments and procedures. All payments will be in the form of cash, check, gift card or clin card, upon completion of each appointment.

TABLE 4: Subject visit and payment overview:

Visit title	VISIT#	Weeks of	Payment (\$)
		completed	
		medication	
Screening	1		50
Baseline	2	0	65
Weekly treatment visit	3	1	25
Biweekly treatment visit	4	3	40
Biweekly treatment visit	5	5	40
Biweekly treatment visit	6	7	40
TARGET DOSE achieved (500mg)			
Biweekly treatment visit- midpoint	7	9	45
assessments. Subjects eligible to			
go to 600mg daily.			
Biweekly treatment visit	8	11	40
Biweekly treatment visit	9	13	40
Endpoint visit	10	16	80
Two weeks post endpoint visit follow	11		15
up (end of medication taper)			
3 month follow up visit	12		30
Total	40		540
Total	12		510

Additional compensation	
Stress script session	40
Stress lab 1	100
Stress lab 2	100
Computer tasks	Up to 40
IVR phone calls	Up to 320 (\$2 per completed phone call plus \$6 for each week where 6 or more calls are completed (up to \$20/week for 16 weeks))
Maximum Total compensation for all visits, labs, and phone calls	1110

FOR ADDITIONAL DETAILS OF SAFETY AND HUMAN SUBJECTS PROTECTION, PLEASE REFER TO THE ATTACHED "HUMAN SUBJECTS" APPENDIX FROM THE GRANT. ALSO, WE HAVE ATTACHED THE CORRESPONDING GRANT APPLICATION FOR MORE INFORMATION.

7. Data and Safety Monitoring Board

The DSMB is composed of persons not otherwise affiliated with the clinical trial who are experienced in various aspects of the conduct of clinical trials for the treatment of addictive disorders. The DSMB for this study had been composed of three investigators located in Connecticut (at Yale) who are not directly involved in this trial – [name]., Ph.D., [name]., and [name]., as the membership of the DSMB. These three clinicians have appropriate expertise in substance abuse and psychopharmacology for this study. None of three are directly involved with this proposed trial and consequently should not pose a conflict of interest. All are faculty at Yale. DSMB members have been transitioned to a VCU faculty composed board and members include Drs. [name], [name] and [name], who are not directly involved in this trail. These clinicians have appropriate expertise in clinical trials and with expertise in substance abuse and psychopharmacology.

Review will occur every 6 months. The DSMB will review any serious and unanticipated events, also severe adverse events and patterns. Additional items may be review like issues with dropouts or early terminations, data issues.

TABLE 5: Abbreviations:

AADUD	Alcohol Dependence Use Disorder – Measures effects of alcohol on life using DSM V criteria
AEQ	Alcohol Expectations Questionnaire - Measure of number of drinks subjects report are needed to produce typical alcohol effects (alcohol sensitivity)
AUQ	Alcohol Urge Questionnaire – Assesses alcohol cravings
BART	Balloon Analogue Risk Task- Assesses reward vs loss to assess risk-taking behavior
BIS	Barratt Impulsiveness Scale -Impulsivity Scale- self-reported measures of impulsive personality traits
BLT	Brown Location Test - Visual learning task independent of verbal, global intellectual, fine motor or drawing skills that consists of five recall learning trials, an interference trial, and a short delay recall
CAPS-5	Clinician Administered PTSD Scale for DSM-5 – Measures symptoms of PTSD
CGI-I	Clinical Global Impression – improvement – Assesses for improvement in baseline since initiation
CGI-S	Clinical Global Impression – severity – To rate severity of patient mental illness
CIWA	Clinical Institute Withdrawal Assessment - Assesses for symptoms of withdrawal
C-SSRS	Columbia Suicide Severity Rating Scale – Suicidal ideation and behavior rating scale
DMQ	Drinking Motives Questionnaire – Assesses personal motives for drinking alcohol
FHAM	Family History Assessment Model – Assesses for psychiatric disorders among relatives of participant
IVR	Interactive Voice Response – A phone system used for self-reporting predetermined questions
LSCR	Lifetime Stressor Checklist – Revised - Self-report measure that assesses traumatic or stressful life events
ММ	Medical Management- A method of conducting a patient visit based on a theoretical paradigm to evaluate adherence to medications and adherence to treatment
MED-Q	Medication Questionnaire- Assesses the participant's belief as to their treatment condition
PCL-5	PTSD Checklist for DSM 5 – Assesses for presence of PTSD symptoms
PHQ-9	Physician's Health Questionnaire - 9-item self-report measure of depressive symptoms with a total score of 0-27
PSS	Perceived Stress Scale - Ten item scale measuring perceived stress
Q-LES-Q	Quality of Life Enjoyment and Satsfaction Questionnaire - Assesses quality of life in subjects
RAND SF-12	RAND (Research AND development) 12 Item Short Form Health Survey – Assesses personal habits and views on personal health
SAFTEE	Systematic Assessment for Treatment of Emergent Effects - Measure of adverse events

V.6 05Jun2020 23

SCID Section E	Structured Clinical Interview - Assesses for substance abuse disorders according to DSM V
SCID-II (antisocial)	Structured Clinical Interview - Assesses Conduct Disorder and Antisocial Personality Disorder Criteria
SCID V	Structured Clinical Interview - Classifies patients according to the presence or absence of standard psychiatric disorders according to DSM-5 criteria
SIP	Short Inventory of Problems – Evaluates experiences of drinkers over past 3 months
SLEI	Stressful Life Event Inventory – Evaluation of stressful life event occurrences over the past month
SORT	Slosson Oral Reading Test- evaluates English reading level
SRE	Self Rating Effects of Alcohol – Self-reported numeric responses to number of drinks needed to achieve certain effects
STAI	State-Trait anxiety Inventory - Measures state and anxiety level
TIPI	Ten item personality inventory – Assesses personality traits
TLFB	Timeline Follow-back- Estimates past 90-day drinking

REFERENCES

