Specific Aim 1) To evaluate fully the efficacy of and scope of effectiveness for ZNS in treating AUDs by adding a civilian arm (*N*=160 randomized, 80 on ZNS and 80 on placebo) to the CSR&D-funded study in veterans, using the same primary outcome (drinks per week) and secondary measures of drinking behavior as the veteran arm [i.e., heavy drinking days/week, percentage of subjects with no heavy drinking days (PSNHDD), craving, reductions in GGT]. Subjects will meet criteria for an AUD (DSM-5) and be heavy drinkers similar to the participants in the VA study. We hypothesize that ZNS will produce a significantly greater reduction in drinks per week than placebo (primary outcome alpha = .05). We also hypothesize that ZNS will significantly improve secondary measures of drinking (corrected for multiple comparisons). We will recruit civilians from the University of Connecticut Health Center (UCHC) and VCU's Institute for Drug and Alcohol Studies (IDAS)

Specific Aim 2) To use telephone-based daily process data collection to elucidate the mechanism of action of ZNS as it relates to changes in craving, anxiety, and genetic variation. This method has been shown to elucidate the mechanism of action of topiramate, as well as its pharmacogenetic interactions. We hypothesize that ZNS' effects will be moderated by genetic variation, craving, and anxiety, but mediated through changes in self-efficacy to reduce heavy drinking.

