6.E.1. Visit 1 (Screening Visit): At the screening visit (visit 1), patients will be asked to provide informed consent. The PI and/or the study Nurse Practioner (NP) will obtain a medical and psychiatric history, and perform a physical exam. Substance use data for the 90 days prior to the screening visit will be collected via the Timeline Follow-Back (TLFB) Method. Blood or saliva and urine samples will be taken for routine clinical laboratory evaluations (including GGTP, ETG/ETS, and PEth), drug screening, pregnancy testing (in females of reproductive potential), and DNA extraction. All projected amounts will be discussed in the consent form, we estimate the total amount of blood drawn to be approximately 10 TBSP for the entire study, but additional labs may need to be repeated at the discretion of the PI to ensure participant health and safety. Additional blood will only be drawn if determined medically necessary. Screening will last about 3-4 hours total.

6.E.2. Visit 2a (Baseline Visit): After the screening visit, eligible patients will undergo the baseline visit prior to randomization. They will complete a packet of questionnaires and the research assistant will train them to record data on alcohol consumption, medication administration and other daily variables using IVR, which is a self-reported assessment of mood, drinking habits and attitudes towards alcohol. Baseline impulsivity will also be measured before imagery using the Barrett Impulsivity Scale [51]. The subject begins a 7-week titration phase, during which the ZNS (or matching PLC) dosage will be titrated up as indicated below in Table 1, to a maximum of 600mg/day. Subjects will receive compensation for all visits, including follow-up visits (see Table 4). Compensation will not be prorated. Participants will be offered transportation assistance if needed to return home from study visits in the form of bus tickets or taxi rides, as long as these trips are within a 20 mile radius or are on the bus lines. Study staff will work with the participant at individual study visits to determine which mode of transportation is most feasible for the participant.

TABLE 1: Medication Titration Schedule

Week	Placebo	Zonisamide dose
1	One capsule daily	100mg QHS
2	Two capsules daily	200mg QHS
3	Two capsules daily	200mg QHS
4	Three capsules daily	300mg QHS
5	Three capsules daily	300mg QHS
6	Four capsules daily	400mg QHS
7	Four capsules daily	400mg QHS
8-9	Five capsules daily	500mg QHS (Target dose)

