6.G. Assessments: We include measures from different sources (see **Table 2**) to cover the various domains in which alcohol treatment may exert an effect and to corroborate self-reported treatment effects.

Study data will be collected and managed using REDCap electronic data capture tools hosted at VCU. REDCap (Research Electronic Data Capture) is a secure, web-based application designed to support data capture for research studies, providing 1) an intuitive interface for validated data entry; 2) audit trails for tracking data manipulation and export procedures; 3) automated export procedures for seamless data downloads to common statistical packages; and 4) procedures for importing data from external sources [52].

- **6.G.1.** Laboratory/Medical Assessments: These assessments serve to: 1) screen patients for medical exclusion criteria, 2) assess potential adverse effects of ZNS, and 3) corroborate self-reported drinking. Prior to entrance into the study, each patient will receive a physical exam, urinalysis and urine toxicology, CBC, a chemistry panel [which includes electrolytes, liver enzymes (ASAT, ALAT, GGTP), bilirubin, uric acid, BUN, and creatinine], and pregnancy testing. Bicarbonate levels will be every 4 weeks because ZNS can cause metabolic acidosis; pregnancy testing and a CBC will also be repeated at the midpoint, which is planned to be week 9 but may be adjusted per patient visit needs. If a patient reports being pregnant or tests positive, she will immediately be excluded or withdrawn from treatment with medication, referred for obstetric evaluation, and advised to discontinue all drinking. At the midpoint (week 9) and endpoint (week 16), GGTP will be repeated to corroborate self-reported alcohol consumption. The patient will be in the downward titration phase of the medication at this point (See Table 1: Medication Titration Schedule). We will also obtain Ethyl Glucuronide (EtG), Ethyl Sulfate (EtS), and Phosphatidyl Ethanol (PEth) as biomarkers to verify subjective claims of drinking during the study.
- **6.G.2. Psychological/Behavioral Assessments:** ZNS is hypothesized to have its greatest influence on alcohol consumption. The assessments listed below measure multiple outcome criteria, because a reduction in drinking may not result in improvement in other domains.

Table 2: Schedule of Assessments

Table 2: Sch				Study Week								
	SC	BL	1	3	5	7	9	11	13	16	18	28
Surveys/Procedures												
Overview and Consent	Х											

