- a. Alcohol use patterns: The Timeline Follow-back (TLFB) [55] will be used to estimate past 90-day drinking at intake and at every treatment visit going back in time from the last assessment. This interview procedure will provide quantity/frequency of alcohol consumption data for each day during the period prior to the interview. The TLFB is reliable and valid when used by trained interviewers. However, it is less useful than daily measures for detecting patterns of alcohol consumption that vary on a day-to-day basis [56, 57]. The Clinical Global Impression scale (CGI) will be used to assess progress in treatment monthly. The Clinical Institute Withdrawal Assessment (CIWA-Ar) will be used to facilitate assessment of withdrawal, and decisions regarding appropriateness for study entry and continuation with respect to physical dependence will be made based on the judgment of the PI.
- **b. Alcohol craving;** will be assessed at each treatment visit with the Alcohol Urge Questionnaire (AUQ), [58].
- c. Alcohol-related problems: The Short Index of Problems (SIP). The SIP, a 15-item instrument that is a subset of the 50-item DrInC [59], measures alcohol dependence symptoms

V.6 05Jun2020 12

and medical, psychological, social, occupational, and legal problems. To reduce respondent burden, we chose to use the SIP which, like the DrInC, measures a single factor of alcohol-related problems (61). The Quality of life enjoyment and satisfaction survey (Q-LES-Q)[60] (REF) will be used to assess quality of life in subjects.

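### The models for drinks/week, GGTP change, AUQ and SIP adjust for past-month heavy drinking days but not for the outcome's own baseline, and the week terms for SIP cannot be estimated

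*Combined protocol and SAP*

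**What the plan says.** Specific Aim 1 is framed as a reduction: "We hypothesize that ZNS will produce a significantly greater reduction in drinks per week than placebo". Section 6.K.1.a fits a mixed model to drinks per week with medication, week and their interaction, and focuses on the last 8 weeks of treatment. Its one baseline covariate is stated as "We will include pre-treatment drinking behavior (past month HDD) as a covariate".

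Section 6.K.2 uses the same covariate for HDD/week, GGTP change, AUQ and SIP, and the same structure for all of them: "For each of these outcome measures, the model will include fixed effects for medication group, week, and the interaction between medication and week". Section 6.K.1.a also proposes to "identify baseline differences between groups that may have occurred despite randomization", but states no adjustment for what is found.

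The own baselines are all collected:

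- **Drinks/week.** On the timeline follow-back (TLFB), section 6.G.5.a says: "This interview procedure will provide quantity/frequency of alcohol consumption data for each day during the period prior to the interview". Section 6.E.1 has it cover the 90 days before screening.
- **GGTP.** It is measured at screening (6.E.1). Section 6.G.1 adds: "At the midpoint (week 9) and endpoint (week 16), GGTP will be repeated to corroborate self-reported alcohol consumption".
- **AUQ and SIP.** Both are taken at the baseline visit (Table 2).

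Table 2 schedules SIP at baseline, week 16 and week 28 only. Table 5 gives SIP a 3-month recall period.

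**The concern.** HDD is a count of days above a threshold, which section 6.K sets at more than 4 drinks for men. A man who drinks 5 every day (5 × 7 = 35 per week) and one who drinks 15 every day (15 × 7 = 105 per week) have the same HDD value. The covariate therefore leaves unexplained part of the between-patient variation that baseline drinks/week could explain, and it corrects only part of any chance imbalance in that baseline. Section 6.E.4 stratifies randomization by site and antidepressant/psychotropic use, not by drinking, so the design does not remove such an imbalance either.

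For AUQ and SIP, HDD is a less direct stand-in still, since craving and alcohol-related problems are different constructs. GGTP is analysed as a change, so its baseline enters by subtraction, which in large samples is never more precise than using it as a covariate.

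Two models are not affected. In the HDD/week model, past-month HDD already is the outcome's baseline. The logistic model for no heavy drinking days (PSNHDD) does not use HDD.

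At stake is the precision of the primary and three secondary comparisons, most of all if dropout approaches the 30% bound in 6.K.7. For SIP there is also a model that cannot be fitted as written.

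**Working it through.** **1. The plan's own figure.** Inputs from 6.K.7 and 6.K.1.a: d = 0.5, N = 128 (160 less 20%), so 64 per arm, α = 0.05. Two-sided testing is stated for PSNHDD and assumed here. Noncentral t with no covariate gives power 0.801, so the stated figure reproduces. With 30% dropout, 80 × 0.70 = 56 per arm and power is 0.746.

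**2. Drinks/week.** No correlations are in the documents, so all of those below are assumed. Let r_own and r_HDD be the correlations of baseline drinks/week and of past-month HDD with on-treatment drinks/week, and r12 their correlation with each other. If HDD adds nothing once baseline drinks/week is known, the effective sample-size ratio of the amended model to the planned one is

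(1 − r_HDD²) / (1 − r_own²), with r_HDD = r_own × r12.

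| r_own | r12 | r_HDD | Ratio |
|---|---|---|---|
| 0.5 | 0.9 | 0.45 | 0.7975/0.75 = 1.06 |
| 0.5 | 0.8 | 0.40 | 0.84/0.75 = 1.12 |
| 0.5 | 0.6 | 0.30 | 0.91/0.75 = 1.21 |
| 0.6 | 0.9 | 0.54 | 0.7084/0.64 = 1.11 |
| 0.6 | 0.6 | 0.36 | 0.8704/0.64 = 1.36 |

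The gain is 6–36%, or a standard error 3–14% smaller (1 − 1/√ratio).

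Choosing the two correlations freely (r_HDD 0.3–0.4, r_own 0.5–0.6) gives 0.84/0.75 = 1.12 to 0.91/0.64 = 1.42.

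If both predict equally (0.5 each, r12 = 0.8), then R² = (0.25 + 0.25 − 2 × 0.25 × 0.8)/(1 − 0.64) = 0.278. The ratio is 0.75/0.722 = 1.04, a 4% gain.

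**3. Power for drinks/week.** Reading d = 0.5 as unadjusted and using d/√(1 − R²), the first set of assumptions (HDD predicting only through baseline drinks/week) gives:

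| Per arm | Planned model (HDD) | With own baseline |
|---|---|---|
| 64 | 0.84–0.915 | 0.90–0.94 |
| 56 | 0.785–0.876 | 0.857–0.906 |

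**4. GGTP change.** With equal variances and HDD ignored, the change-score to ANCOVA variance ratio is 2(1 − r)/(1 − r²):

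- r = 0.6: 0.80/0.64 = 1.25
- r = 0.7: 0.60/0.51 = 1.18
- r = 0.8: 0.40/0.36 = 1.11

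**5. AUQ and SIP.** With r_HDD = 0.2 the numerator is 1 − 0.04 = 0.96:

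- r_own = 0.4: 0.96/0.84 = 1.14
- r_own = 0.5: 0.96/0.75 = 1.28
- r_own = 0.6: 0.96/0.64 = 1.50
- r_own = 0.7: 0.96/0.51 = 1.88

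**6. SIP week terms.** The fixed effects are intercept, group, week, group × week and HDD, five columns with week taken as linear. With week 16 as the only response time, week is a multiple of the intercept and group × week a multiple of group, so the rank is 3 of 5. AUQ (weeks 9, 11, 13, 16) and GGTP (weeks 9, 16) both give rank 5 of 5.

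**7. SIP recall.** Three months is about 13 weeks. Of the period recalled at week 16, 13 − 8 = about 5 weeks precede the analysis window.

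**The case against.** The strongest reply is that nothing in the primary analysis is invalid. The plan pre-specifies a prognostic drinking covariate, its power claim holds with no covariate, and choosing a better one is a matter of efficiency. That is right, and the point is put only as forgone precision.

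The size for drinks/week is also uncertain. Past-month HDD and drinks/week come from the same TLFB and probably overlap heavily, so the gain could be as small as 4%. This stands.

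The power values need three qualifications:

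- The 0.746 at 56 per arm is a no-covariate benchmark. The planned HDD model does better (0.785–0.876 under the assumptions in the working).
- Fifty-six per arm is a worst case. Patients are followed after stopping medication, dropouts contribute data until they leave, and the protocol expects dropout below 30%.
- Section 6.K.7 does not say whether d = 0.5 is adjusted. If it applies to the HDD-adjusted SD, a middle case (r_own 0.5, r12 0.8) moves power only from 0.807 to 0.849 (normal approximation). The sample-size ratios do not depend on this reading.

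The GGTP range applies only if change means a change score, which the text suggests but does not settle. For SIP, the week terms would become estimable if baseline or week 28 were modelled as a response. The plan says neither, and week 28 lies after treatment. The group contrast at week 16 remains estimable, so the SIP defect concerns specification and does not produce a wrong result.

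**Conclusion.** The concern holds. Four models omit a collected own-baseline covariate: drinks/week, GGTP change, AUQ and SIP. The cost is precision, not validity, and the plan's power statement is not in doubt.

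The omission is certain from the text. Its size is not, because every correlation is assumed. A worthwhile gain on the primary outcome is plausible but not assured, and AUQ and SIP probably stand to gain most. Because the change needs no new data, it should be made even if the gain on drinks/week proves small.

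The SIP mismatch follows from the visit schedule and depends on no assumed correlation. With one value per patient during treatment, the week and medication-by-week terms cannot be estimated as specified.

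**What to change.** - **Drinks/week:** add TLFB baseline drinks/week to the primary model. Past-month HDD may stay.
- **GGTP change:** add screening GGTP as a covariate.
- **AUQ:** add baseline AUQ.
- **SIP:** replace the repeated-measures model with ANCOVA of the week-16 score on treatment and baseline SIP, without week terms. State that the 3-month recall still reaches into titration, which ANCOVA does not remove.
- **HDD/week and PSNHDD:** leave as they are.
- **Pooled analysis:** specify the same covariates for the combined analysis with the veteran data.

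Fix these covariates in the SAP before unblinding, so that the planned check of baseline differences does not drive the choice of adjustment. No new data or visits are needed. The cost is SAP wording plus alignment with the veteran study's model, whose analysis plan is not in these documents and has to be consulted first.
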